2.5 RISK/BENEFIT ASSESSMENT

2.5.1 KNOWN POTENTIAL RISKS

Risks of radiation include the following acute toxicities:

- Generalized fatigue, malaise, anorexia
- Skin changes
- Site specific toxicities include difficulty swallowing, shortness of breath, loss of appetite, nausea/vomiting, bowel cramping, loose stool or diarrhea.
- Late toxicities of GI ulceration or obstruction, esophageal stricture, pneumonitis, renal toxicity, liver toxicity, bone weakening.

Risks of olaparib include the following acute toxicities:

- Generalized effect on energy level
- Hematological toxicity (neutropenia, leukopenia, anemia, thrombocytopenia)
- Gastrointestinal toxicity (nausea, vomiting, diarrhea)
- Pulmonary toxicity (dyspnea, infection)
- Renal toxicity

Risks of pembrolizumab include the following toxicities:

- Pneumonitis
- Diarrhea/Colitis
- AST/ALT elevation or increased bilirubin
- Type 1 diabetes mellitus (T2DM) or Hyperglycemia
- Hypophysitis
- Hyperthyroidism
- Hypothyroidism
- Nephritis and renal dysfunction

- Myocarditis

These immune-related AEs (irAEs) may occur shortly after the first dose or several months after the last dose of pembrolizumab treatment and may affect more than one body system simultaneously.

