6 STUDY INTERVENTION

6.1 STUDY INTERVENTION(S) ADMINISTRATION

Potential trial patients will be pre-identified at participating centers into two cohorts:

- (1) germline or somatic deleterious mutation involving genes critical to the DNA repair through homologous recombination deficiency (HRD), as demonstrated by Next-generation DNA sequencing in a CLIA certified, CAP tested and bioinformatics-validated testing lab prior to enrollment. This could include, but not be limited to one of the following genes: *ARID1A*, *ATM*, *ATR*, *MRE11A*, *NBN*, *PTEN*, *RAD50/51/51B*, *BARD1*, *BLM*, *BRCA1*, *BRCA2*, *BRIP1*, *FANCA/C/D2/E/F/G/L*, *PALB2*, *WRN*, *CHEK2*, *CHEK1*, *BAP1*, *FAM175A*, *SLX4*, *MLL2* or *XRCC* and
- (2) no evidence of HR deficiency.

If a pathogenic mutation in the HR pathway is confirmed and not listed above, the study PI will determine if the patient is eligible based on available clinical or pre-clinical literature.

[figure not shown]
The determination of a deleterious mutation must be supported in the documentation included in the testing, and should include clinical, or pre-clinical literature to support the finding that a

specific mutation results in impaired function of the gene, and thus impaired DNA repair through homologous recombination. Mutations and deletions will be evaluated against the Human Gene Mutation database and other online databases (ClinVar, Breast Cancer Information Core, PubMed) to evaluate the functional relevance, and to make a determination on the likelihood of the mutation resulting in defective homologous recombination-dependent DNA repair. Variants of unknown significance will not be eligible.

The testing may have been done at any time prior to enrollment.

Starting C1D1, olaparib 200mg PO BID will be given concurrently with radiation (25 Gy in 5 fractions). Each cycle is 21 days. Starting on C2D1, Pembrolizumab 200mg IV will be administered on Day 1 every 3 weeks with olaparib 300mg PO BID (12 hours apart). There is no specification regarding the sequence in which the drugs should be given on days when they are administered together. For Cycle 1, patients will be evaluated weekly for 3 weeks with blood tests, clinic visits, and physical exams. Starting Cycle 2, patient will be evaluated every 3 weeks on Day 1 of each cycle.

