6.1.2 DOSING AND ADMINISTRATION

The treatment to be used in this trial is outlined below:

Drug	Dose/Potency	Dose Frequency	Route of Administration	Regimen/Treatment Period	Use
Pembrolizumab	200 mg	Q3W	IV infusion	Day 1 of each 3 week cycle (excluding Cycle 1)	Experimental
Olaparib*	200mg PO BID	daily	PO	Daily during Radiation D1-21	Experimental
Olaparib*	300mg PO BID	daily	PO	Daily Post-Radiation	Experimental
SBRT	25Gy in 5 fractions	daily M-F	N/A	5 days starting Day 1	Experimental

*During radiation portion, Olaparib dose will be 200mg PO BID. When combined with pembrolizumab, Olaparib dose will be 300mg PO BID.

Trial treatment should begin on the day of treatment (Combination SBRT and Olaparib)

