APPENDIX 5: DOSE MODIFICATION AND TOXICITY MANAGEMENT FOR OLAPARIB

Any toxicity observed during the course of the study could be managed by interruption of the dose of study treatment or dose reductions. Repeat dose interruptions are allowed as required, for a maximum of 4 weeks on each occasion. If the interruption is any longer, the study team must be informed. Study treatment can be dose reduced to 250 mg twice daily as a first step and to 200 mg twice daily as a second step. If the reduced dose of 200 mg twice daily is not tolerable, no further dose reduction is allowed and study treatment should be discontinued. Once dose is reduced, escalation is not permitted.

RENAL IMPAIRMENT

If after study entry and while still on study therapy, a patient's estimated CrCl falls below the threshold for study inclusion (≥ 51 ml/min), retesting should be performed promptly.

A dose reduction is recommended for patients who develop moderate renal impairment (calculated creatinine clearance by Cockcroft-Gault equation of between 31 and 50 ml/min) for

any reason during the study: the dose of olaparib should be reduced to 200mg twice daily.

Because the CrCl determination is only an estimate of renal function, in instances where the CrCl falls to between 31 and 50 mL/min, the investigator should use his or her discretion in determining whether a dose change or discontinuation of therapy is warranted.

Olaparib has not been studied in patients with severe renal impairment (creatinine clearance ≤ 30 mL/min) or end-stage renal disease; if patients develop severe impairment or end stage disease is it recommended that olaparib be discontinued

MANAGEMENT OF HEMATOLOGICAL TOXICITY

Management of anemia

Table 5: Management of anemia

Anemia	Management/Next Dose for olaparib
\leq Grade 1 Grade 2	Give appropriate supportive treatment and investigate causality. Investigator judgement to continue olaparib with supportive treatment (eg transfusion) or interrupt dose for a maximum of 4 weeks. If repeat Hb < 10 but ≥ 8 g/dl , dose interrupt (for max of 4 weeks) until Hb ≥ 10 g/dl and upon recovery dose reduction to 250 mg twice daily as a first step and to 200 mg twice daily as a second step may be considered.

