Grade 3 Grade 4	Give appropriate supportive treatment (e.g. transfusion) and investigate causality. Interrupt olaparib for a maximum of 4 weeks. until improved to Hb ≥ 10 g/dl. Upon recovery dose reduce to 250 mg twice daily as a first step and to 200 mg twice daily as a second step in the case of repeat Hb decrease.

*Patients requiring a delay of >4 weeks should go off protocol therapy. The Study Principal Investigator should be consulted for possible resumption of treatment at a lower dose for patients who showed disease response.

**Patients requiring > two dose reductions should go off protocol therapy.

Management of neutropenia, leukopenia, and thrombocytopenia

Table 6: Management of neutropenia, leukopenia and thrombocytopenia

Neutropenia/leukopenia/thrombocytopenia	Management/Next Dose for olaparib
≤ Grade 1 Grade 2	Investigator judgement to continue treatment or if dose interruption, this should be for a maximum of 4 weeks; appropriate supportive treatment and causality investigation
Grade 3 Grade 4	Dose interruption until recovered to CTCAE gr 1 or better for a maximum of 4 weeks. If repeat CTCAE grade 3-4 occurrence, dose reduce olaparib to 250 mg twice daily as a first step and 200 mg twice daily as a second step

*Patients requiring a delay of >4 weeks should go off protocol therapy. The Study Principal Investigator should be consulted for possible resumption of treatment at a lower dose for patients who showed disease response.

**Patients requiring > two dose reductions should go off protocol therapy.

Adverse event of neutropenia and leukopenia should be managed as deemed appropriate by the investigator with close follow up and interruption of study drug if CTCAE grade 3 or worse neutropenia occurs.

Primary prophylaxis with Granulocyte colony-stimulating factor (G-CSF) is not recommended, however, if a patient develops febrile neutropenia, study treatment should be stopped and appropriate management including G-CSF should be given according to local hospital guidelines. Please note that G-CSF should not be used within at least 24 h (7 days for pegylated G-CSF) of the last dose of study treatment unless necessary.

Platelet transfusions, if indicated, should be done according to local hospital guidelines. For cases where patients develop prolonged hematological toxicity (≥2 week interruption/delay in study treatment due to CTCAE grade 3 or worse), refer to Section 5.2.2.3.3

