Events of nausea and vomiting are known to be associated with olaparib treatment. In study D0810C00019 nausea was reported in 71% of the olaparib treated patients and 36% in the placebo treated patients and vomiting was reported in 34% of the olaparib treated patients and 14% in the placebo treated patients. These events are generally mild to moderate (CTCAE grade 1 or 2) severity, intermittent and manageable on continued treatment. The first onset generally occurs in the first month of treatment for nausea and within the first 6 months of treatment for vomiting. For nausea, the incidence generally plateaus at around 9 months, and for vomiting at around 6 to 7 months.

No routine prophylactic anti-emetic treatment is required at the start of study treatment, however, patients should receive appropriate anti-emetic treatment at the first onset of nausea or vomiting and as required thereafter, in accordance with local treatment practice guidelines. Alternatively, olaparib tablets can be taken with a light meal/snack (ie 2 pieces of toast or a couple of biscuits).

As per international guidance on anti-emetic use in cancer patients (ESMO, NCCN) generally a single agent antiemetic should be considered eg dopamine receptor antagonist, antihistamines or dexamethasone.

Table 7: Management of nausea

Nausea	Management/Next Dose for olaparib
≤ Grade 1	No change in dose
Grade 2	Hold until ≤ Grade 1. Resume at same dose level
Grade 3	Hold* until <Grade 2. Resume at one dose level lower, if indicated.**
Grade 4	Off protocol therapy

*Patients requiring a delay of >4 weeks should go off protocol therapy. The Study Principal Investigator should be consulted for possible resumption of treatment at a lower dose for patients who showed disease response.

**Patients requiring > two dose reductions should go off protocol therapy.

Table 8: Management of vomiting

Vomiting	Management/Next Dose for olaparib
≤ Grade 1	No change in dose
Grade 2	Hold until ≤ Grade 1. Resume at same dose level
Grade 3	Hold* until <Grade 2. Resume at one dose level lower, if indicated.**
Grade 4	Off protocol therapy

*Patients requiring a delay of >4 weeks should go off protocol therapy. The Study Principal Investigator should be consulted for possible resumption of treatment at a lower dose for patients who showed disease response.

**Patients requiring > two dose reductions should go off protocol therapy.

Table 9: Management of diarrhea

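### Appendix 5's olaparib steps (250 then 200 mg BID) assume a 300 mg start and cannot work as reductions in Cycle 1; its renal dose rule also misses patients who enter with CrCl 31–50 mL/min

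*Combined protocol and SAP*

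**What the plan says.** Section 6.1 sets the Cycle 1 dose: "Starting C1D1, olaparib 200mg PO BID will be given concurrently with radiation". The footnote to the table in Section 6.1.2 sets both phases: "During radiation portion, Olaparib dose will be 200mg PO BID. When combined with pembrolizumab, Olaparib dose will be 300mg PO BID". Cycles last 21 days.

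Appendix 5 opens without limiting itself to either phase: "Any toxicity observed during the course of the study could be managed by interruption of the dose of study treatment or dose reductions". It continues "Study treatment can be dose reduced to 250 mg twice daily as a first step", with 200 mg BID as the second step. If the reduced 200 mg dose is not tolerated, olaparib stops. A reduced dose may not be raised again.

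The tables in Appendix 5 apply the ladder as follows:

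- **Table 5, grade 3–4 anemia:** hold for at most 4 weeks until Hb is at least 10 g/dL, then "Upon recovery dose reduce to 250 mg twice daily as a first step". This applies after a first event. In the grade 2 row the same step is optional.
- **Table 6, other cytopenias:** "If repeat CTCAE grade 3-4 occurrence, dose reduce olaparib to 250 mg twice daily as a first step".
- **Tables 7–9, grade 3 nausea, vomiting and diarrhea:** "Resume at one dose level lower, if indicated".

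On renal function, Appendix 5 recites an inclusion threshold of CrCl at least 51 mL/min. It recommends 200 mg BID for patients who develop CrCl 31–50 mL/min during the study, subject to investigator discretion. Table 1 in Section 5.1 instead admits creatinine up to 1.5 x ULN with no CrCl floor, or CrCl of at least 30 mL/min when creatinine is higher.

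**The concern.** A ladder in absolute doses works only from a starting dose above its first step. That is true from C2D1 (300 mg) but not in Cycle 1 (200 mg), where the first step lies above the current dose and the second equals it. Cycle 1 is the SBRT–olaparib combination that the safety lead-in exists to check. A site treating grade 3–4 anemia in that cycle would find a directive instruction that cannot be followed as a reduction, and no other restart dose.

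The renal text has a related gap. Two sections state different entry limits, and the dose recommendation covers impairment that arises on study but not the same impairment at entry. At stake are the dosing of individual patients and consistency between sites, not the trial's inference.

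**Working it through.** The plan gives no figure of its own to reproduce here. The check is dose arithmetic and a cross-read of sections.

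**Inputs.** Cycle 1 dose 200 mg BID and 300 mg BID from C2D1 (Sections 6.1, 6.1.2). Ladder 250 then 200 mg BID, maximum hold 4 weeks, restart at Hb ≥10 g/dL (Appendix 5). Entry Hb ≥9.0 g/dL (Table 1). CBCs on Days 8 and 15 of Cycle 1 (Section 1.3). Treatment allowed up to 7 days before or after scheduled Day 1 after Cycle 1 (Section 6.1.3.1).

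**1. Ladder against each phase.**
- Against 200 mg: first step 250/200 − 1 = +25%; second step 200/200 − 1 = 0%.
- Against 300 mg: first step 250/300 − 1 = −16.7%; second step 200/300 − 1 = −33.3%.

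The steps are reductions only against 300 mg.

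**2. Can the Table 5 case arise in Cycle 1?** Section 2.5.1 lists "Hematological toxicity (neutropenia, leukopenia, anemia, thrombocytopenia") among the olaparib risks. The grade 2 row of Table 5 ends at 8 g/dL. The margin from the entry limit is 9.0 − 8.0 = 1.0 g/dL, so a fall of just over that reaches the grade 3–4 row. The Day 8 and Day 15 counts would detect it.

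**3. When would the restart fall?** C2D1 is nominally Day 22, and the window makes it Day 15 to Day 29.
- Event found on Day 8: 22 − 8 = 14 days to C2D1 (range 7 to 21).
- Event found on Day 15: 22 − 15 = 7 days to C2D1 (range 0 to 14).
- A full 28-day hold ends on Day 36 or Day 43, after C2D1 in every case.

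Both orders are therefore possible. Before C2D1, 250 mg is 25% above the scheduled 200 mg. After C2D1, it is 16.7% below the scheduled 300 mg, but still 25% above the dose at which the anemia occurred.

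**4. Other tables.** Table 6 uses the ladder only for a repeat grade 3–4 event. Within Cycle 1 that needs an event, recovery to grade 1, a restart and a second event, so it is barely reachable. Tables 7–9 call for a lower level that the ladder does not contain below 200 mg, though they add a qualifier leaving room for judgment.

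**5. Renal.** Take a patient entering with CrCl 40 mL/min and creatinine within 1.5 x ULN. Table 1 admits this patient; the limit recited in Appendix 5 would not. The 200 mg recommendation is worded for patients who develop CrCl 31–50 mL/min, and the discretion clause for values that fall into that range. Neither describes a patient already there. The schedule gives 300 mg BID from C2D1: 300/200 − 1 = +50% against the dose recommended for the same CrCl acquired on study. In Cycle 1 everyone takes 200 mg, so the gap begins at C2D1.

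**6. What does not change.** Section 9.2 (26 patients, ORR 0.25 against 0.45) does not use the ladder. In the lead-in, a clinically significant, at least possibly related grade 3–4 anemia counts as a DLT when it occurs, before any restart (Section 6.1.1).

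**The case against.** The strongest reply is that no competent site would raise the dose. Table 5 tells the site to reduce, the surrounding text forbids escalation after a reduction, and 200 mg is the bottom of the ladder with discontinuation below it. This stands as evidence of intent: 250 mg was evidently written for a 300 mg start. A reader might infer that the protocol orders an escalation after severe anemia; the wording does not support that. But this reply leaves Cycle 1 with no restart dose. The discontinuation sentence does not clearly fill the gap, because it concerns 200 mg reached by reduction, whereas in Cycle 1 it is the planned dose.

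Second, every patient is due to rise to 300 mg, so 250 mg after C2D1 is a real reduction from the assigned dose. That is correct, and the 25% excess over the scheduled dose applies only to a restart before C2D1. That case is narrow: Hb must recover to at least 10 g/dL, above the 9.0 g/dL entry limit, within the Cycle 1 window.

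Third, other safeguards exist. Laboratory results must be acceptable before each dose (Section 8.1.3), Table 5 requires the cause to be investigated, and Section 7.2 lets the investigator stop treatment for risk. These limit harm, but none supplies a dose.

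On renal function, a reader might infer that patients impaired at entry have no renal protection at all. That goes too far. The recommendation to discontinue if CrCl falls to 30 mL/min or below still covers decline on study, and the 200 mg rule is itself only a recommendation. The note under Table 1 allowing local adaptation concerns eligibility laboratory values and gives no olaparib dose.

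**Conclusion.** The point holds as a defect in the text of a dose-safety rule. The ladder is not limited to the phase it fits, so Table 5's instruction after a first grade 3–4 anemia in Cycle 1 is unworkable as a reduction. The 51 mL/min limit in Appendix 5 contradicts Table 1, and patients entering at CrCl 31–50 mL/min fall outside the 200 mg recommendation.

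Taken literally, the sizes are +25% against the scheduled dose for a restart before C2D1, −17% for a restart after it, and +50% in the renal comparison. They rest on the doses and thresholds as printed and on the nominal Day 22 with its 7-day window. The documents give no rate for these events and none is assumed; with 26 planned patients, few are likely to be affected.

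A reader might also infer that the DLT count or the trial's error rates are compromised, or that 200 mg must be the ceiling from C2D1 after a Cycle 1 event. The documents support neither. The first does not follow from Sections 6.1.1 and 9.2, and the second is a clinical choice that no section makes. It should be fixed because the affected rule protects patients and the correction is easy.

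**What to change.** Amend Appendix 5 and reconcile it with Table 1:

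- Limit the 250/200 mg ladder to the 300 mg phase.
- For Cycle 1, state: hold, then resume at no more than 200 mg BID, or discontinue.
- State the C2D1 dose after such a Cycle 1 event. It should be below 300 mg BID; the choice between 200 and 250 mg belongs to the investigators.
- Use one CrCl entry threshold in place of the present 51 and 30 mL/min, and say whether it also applies when creatinine is within 1.5 x ULN.
- If patients with CrCl 31–50 mL/min remain eligible, apply the 200 mg BID recommendation to them from C2D1, with the same investigator discretion.

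The cost is a short text amendment and slightly lower olaparib exposure in a few patients. If the threshold is settled at 51 mL/min, some patients whom Table 1 now admits would be excluded. Visits, DLT rule, sample size and analysis stay as they are.

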- b. For patients within whom a deleterious mutation in the homologous recombination pathway is found, the determination of a deleterious mutation must be supported in the documentation included in the testing, and should include clinical, or pre-clinical literature to support the finding that a specific mutation results in impaired function of the gene, and thus impaired DNA repair through homologous recombination. Variants of unknown significance will not be eligible.
 - c. Patients with germline deleterious mutations may have been identified at any time point prior to inclusion in the protocol and do NOT need to have this genetic testing repeated regardless of time frame and intervening therapy.
8. Participants must have received at least one line of therapy including a fluoropyrimidine and platinum drug. For participants with HER2+ tumors, they must have received trastuzumab. Adjuvant therapy does not count toward first-line therapy unless patient recurs within 6 months of completion.
 9. Have an Eastern Cooperative Oncology Group (ECOG) performance status of 0 to 1.
 10. Participants must have the ability to swallow whole pills and liquids at the Screening Visit and, in the investigator's judgement, for the duration of the study.
 11. Have adequate organ function as defined in Table 1

Table 1: Adequate Organ Function Laboratory Values:

System:	Laboratory Value:
Hematological	
Absolute neutrophil count (ANC)	$\geq 1500/\mu\text{L}$
Platelets	$\geq 100\,000/\mu\text{L}$
Hemoglobin	$\geq 9.0\text{ g/dL}$ or $\geq 5.6\text{ mmol/L}^a$
Renal	
Creatinine OR Measured or calculated ^b creatinine clearance (GFR can also be used in place of creatinine or CrCl)	$\leq 1.5 \times \text{ULN}$ OR $\geq 30\text{ mL/min}$ for participant with creatinine levels $> 1.5 \times \text{institutional ULN}$
Hepatic	
Total bilirubin	$\leq 1.5 \times \text{ULN}$ OR direct bilirubin $\leq \text{ULN}$ for participants with total bilirubin levels $> 1.5 \times \text{ULN}$
AST (SGOT) and ALT (SGPT)	$\leq 2.5 \times \text{ULN}$ ($\leq 5 \times \text{ULN}$ for participants with liver metastases)
Coagulation	
International normalized ratio (INR) OR prothrombin time (PT) Activated partial thromboplastin time (aPTT)	$\leq 1.5 \times \text{ULN}$ unless participant is receiving anticoagulant therapy as long as PT or aPTT is within therapeutic range of intended use of anticoagulants

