ALT (SGPT)=alanine aminotransferase (serum glutamic pyruvic transaminase); AST (SGOT)=aspartate aminotransferase (serum glutamic oxaloacetic transaminase); GFR=glomerular filtration rate; ULN=upper limit of normal.

^a Criteria must be met without erythropoietin dependency and without packed red blood cell (pRBC) transfusion within last 2 weeks.

^b Creatinine clearance (CrCl) should be calculated per institutional standard.

Note: This table includes eligibility-defining laboratory value requirements for treatment; laboratory value requirements should be adapted according to local regulations and guidelines for the administration of specific chemotherapies.

12. Participant receiving corticosteroids, for reasons other than radiation related toxicities, may continue as long as their dose is stable (meaning no increase or on tapering dose) for least 4 weeks prior to initiating protocol therapy.
13. Female participants are eligible if they are: not pregnant (within 28 days prior to start of study treatment - see Appendix 3), not breastfeeding, and at least one of the following conditions applies:
 - a.) Not a woman of childbearing potential (WOCBP) as defined in Appendix 3
 - OR
 - b.) A WOCBP who agrees to follow the contraceptive guidance in Appendix 3 during the treatment period and for at least 120 days after the last dose of study treatment.
14. Male participants must agree to use a contraception as detailed in Appendix 3 of this protocol during the treatment period and for at least 120 days after the last dose of study treatment and refrain from donating sperm during this period.

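### Appendix 5 gives 51 mL/min as the CrCl inclusion threshold, but Table 1 admits patients below it, and no renal dose recommendation covers those who enter at 31–50 mL/min

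*Combined protocol and SAP*

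**What the plan says.** **Eligibility (Section 5.1, criterion 11 and Table 1).** The note to the table reads "This table includes eligibility-defining laboratory value requirements for treatment". Creatinine of at most 1.5 × ULN qualifies a patient with no CrCl requirement. The alternative is CrCl of at least 30 mL/min, "for participant with creatinine levels" above 1.5 × ULN. The table adds that "GFR can also be used in place of creatinine or CrCl", and a footnote leaves the CrCl formula to institutional practice.

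**Dose (Sections 6.1, 6.1.2 and 6.1.3.1).** Olaparib is 200 mg BID in Cycle 1 and 300 mg BID from C2D1 with pembrolizumab. None of these sections has a renal qualifier.

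**Renal rule (Appendix 5, Renal Impairment).**
- Retest promptly if the "estimated CrCl falls below the threshold for study inclusion", with 51 mL/min or above given as that threshold.
- "A dose reduction is recommended for patients who develop moderate renal impairment", defined as Cockcroft-Gault CrCl of 31 to 50 mL/min arising during the study. The dose is then 200 mg BID.
- However, "in instances where the CrCl falls to between 31 and 50 mL/min, the investigator should use his or her discretion" on whether to change the dose or stop.
- "Olaparib has not been studied in patients with severe renal impairment" (30 mL/min or below). If a patient develops this, stopping olaparib is recommended.

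**The concern.** Appendix 5 is written as if nobody can enter below 51 mL/min, so it deals only with decline on study. Table 1 does let patients in below 51, and for them the plan is silent. No section gives a Cycle 2 dose for a patient whose CrCl is already 31–50 at baseline. The retest sentence does not fit such a patient either, because CrCl cannot fall below a level it never reached.

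What is at stake is dosing safety. Section 2.5.1 lists renal toxicity among the risks of olaparib. The DLT window in Section 6.1.1 runs to Cycle 2 Day 21, so it includes the first weeks at 300 mg BID. If a renally impaired entrant in the six-patient lead-in had a DLT, it would be hard to say whether the combination or an unadjusted olaparib dose was responsible. That consequence is conditional on such a patient being enrolled.

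**Working it through.** The point rests on comparing the texts. The arithmetic only sizes the gap and shows that the creatinine route can admit the patients in question.

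**Step 1. Thresholds.** Appendix 5 gives 51 mL/min and the CrCl arm of Table 1 gives 30 mL/min. The gap is 51 − 30 = 21 mL/min, so the whole 31–50 band can be eligible. Table 1 also admits a CrCl of exactly 30, which Appendix 5 classes as severe.

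**Step 2. Dose for the same CrCl, for example 40 mL/min.**

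| | CrCl 40 develops on study | CrCl 40 present at entry |
|---|---|---|
| Cycle 1 | 200 mg BID | 200 mg BID |
| From C2D1 | 200 mg BID recommended, investigator discretion | 300 mg BID by default, no renal text |

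Daily doses are 2 × 300 = 600 mg and 2 × 200 = 400 mg, a ratio of 600/400 = 1.5. In Cycle 1 there is no difference.

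**Step 3. Can the creatinine route admit CrCl below 51?** Cockcroft-Gault CrCl = (140 − age) × kg / (72 × creatinine in mg/dL), times 0.85 for women. Age, weight and ULN below are assumptions; the documents give none of them. Every row passes Table 1, because creatinine is at most 1.5 × ULN.

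| Assumed patient | ULN (mg/dL) | CrCl at 1.0 × ULN (mL/min) | CrCl at 1.5 × ULN (mL/min) |
|---|---|---|---|
| Man, 60 y, 75 kg | 1.0 | 6000/72.0 = 83.3 | 6000/108.0 = 55.6 |
| Man, 65 y, 70 kg | 1.2 | 5250/86.4 = 60.8 | 5250/129.6 = 40.5 |
| Man, 70 y, 60 kg | 1.3 | 4200/93.6 = 44.9 | 4200/140.4 = 29.9 |
| Woman, 70 y, 50 kg | 1.0 | 2975/72.0 = 41.3 | 2975/108.0 = 27.5 |
| Woman, 70 y, 50 kg | 1.3 | 2975/93.6 = 31.8 | 2975/140.4 = 21.2 |

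For the woman, 70 × 50 × 0.85 = 2975. The first man never drops below 51. The other profiles fall into 31–50 or, at the upper creatinine limit, to 30 or below. The table shows that the route is open, not how often it would be used.

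**The case against.** Several provisions let a careful investigator act. Exclusion criterion 16 allows exclusion for a laboratory abnormality, the Table 1 note asks for adaptation to local guidelines, and Section 8.1.3 requires acceptable results before each dose. These lower the risk, but none states a CrCl cut-off or an olaparib dose. The discretion in Appendix 5 is itself worded for a CrCl that falls. Section 2.4 does describe olaparib at 200 mg every 12 hours throughout, but that is background text, and the three dosing sections agree on 300 mg BID with pembrolizumab.

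A reader might infer that the protocol orders 300 mg BID for renally impaired entrants, or assigns two fixed doses to patients with the same CrCl. The documents do not support that. The 300 mg dose is a general default, and the 200 mg dose is a recommendation the investigator may set aside, so a patient who declines on study might also stay at 300 mg. The contrast is between a discretionary recommendation and silence, and the ratio of 1.5 applies only where the recommendation is followed.

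A reader might also infer that 51 should simply be changed to match Table 1. That would do harm. The figure sits in the retest sentence and works there, just above the 31–50 band. Lowering it to 30 would remove the prompt retest for a fall into that band.

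Finally, the strand at 30 mL/min or below rests on a boundary value and assumed profiles. It stands as an edge case and no more.

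**Conclusion.** The inconsistency is real and should be fixed. Appendix 5 states an inclusion threshold that Table 1 does not contain, and patients who enter at CrCl 31–50 mL/min have no renal dose recommendation. Followed as written, the plan gives them the unreduced default from C2D1: 600 mg/day, against the 400 mg/day recommended when the same CrCl arises on study. Entry at 30 mL/min or below is possible only in edge cases, namely exactly 30 by the CrCl arm, or lower by the creatinine arm.

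The mismatch and the missing baseline rule follow from the text alone. Only the Cockcroft-Gault examples depend on assumptions. How many of the 26 planned patients would be affected cannot be estimated from the documents. Nothing here bears on the sample size, the type I error rate or the power in Section 9.2.

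**What to change.** 1. **Appendix 5, retest sentence.** Keep 51 mL/min as the trigger for retesting and delete its description as the inclusion threshold.
2. **Table 1.** Add a Cockcroft-Gault CrCl floor above 30 mL/min that applies to every patient, including those who qualify by creatinine of at most 1.5 × ULN. Changing the CrCl arm alone would leave the creatinine route open, and the 40.5 and 29.9 mL/min examples would still be admitted.
3. **Appendix 5, dose recommendation.** Extend it, with the same investigator discretion, to patients whose CrCl is 31–50 mL/min at baseline, so that 200 mg BID is their recommended dose from C2D1. Cross-refer to it from Section 6.1.2.

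Alternatively, if 51 mL/min was the intended entry threshold, require it of all patients in Table 1. The on-study rule in Appendix 5 can then stay as it is.

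The cost is a short amendment, plus a lower olaparib dose or exclusion for any patients in this range. Those held at 200 mg BID would have no toxicity step left: "If the reduced dose of 200 mg twice daily is not tolerable, no further dose reduction is allowed".
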